Randomization and blinding

[name] will oversee the allocation of the participants to the control or treatment group and will be the only researcher who will not be blinded as to the experimental condition to which each participant belongs.

Participants will be allocated to the control or treatment group according to a pre-generated sequence of pseudorandom numbers, although deviations from this sequence may be made in order to ensure that the two groups are approximately matched in severity of symptoms. After prism adaptation training [name] will give the participant the set of goggles that they will be using for their sham/real prism adaptation treatment. The goggles will be handed to the participant in a sealed, opaque bag so that none of the other researchers will be able to see what kind of goggles the participant has been given. The participant will be instructed to seal the goggles in the same bag when they bring them back to the Dartmouth Hitchcock Medical Centre at the end of the treatment period. [name] will not be involved in any of the pre- or post-treatment assessments. In order to gauge progress an initial analysis will be performed once 60% of the participants have completed the post-treatment assessment, in which case the other researchers will be unblinded as to the group membership of the participants who have already completed the main components of the study. Aside from [name], the remaining members of the research team will be blind as to the group membership of the remaining 40% of participants.

Prism adaptation

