Falls Efficiency Scale. This ten-item self-report questionnaire asks people to rate their confidence in performing daily activities without falling. Responses are given on a scale from 0 ("very confident") to 10 ("not very confident") and a total score out of 100 is computed.

Activities-specific Balance Confidence Scale. This 16-item self-report questionnaire is similar to the Falls Efficiency Scale, but has greater sensitivity to gait impairments in more ambulatory patients.

PDQ-39 (mobility and activities of daily living sections). This self-report questionnaire is the most widely-used Parkinson's Disease specific measure of health and daily function. Participants indicate the extent to which they have experienced problems with different aspects of mobility and self-care. Each item is scored from 0 ("never have problems") to 4 ("always have problems"), and a percentage is calculated.

New Freezing of Gait Questionnaire. This nine-item questionnaire detects and evaluates the impact and severity of freezing of gait on locomotion and daily activities.

The following questionnaire will be administered in the pre-test only:

Patient-Centered Outcome Questionnaire – Parkinson's Disease. This four-item questionnaire measures patient's expectations of treatment outcome. The data from this questionnaire will be used in post-hoc analysis to regress out any potential effects of patient expectation (e.g. placebo effect) on perceived improvements.

The following questionnaire will be administered in the post-tests only:

Post-intervention questionnaire. This questionnaire asks questions specific to the participant's experience of the prism adaptation treatment. There are two versions of this questionnaire. Version 1 is to be administered in visit 2. In Version 1 the participant is asked to rate the extent to which they felt any adverse effects, the

degree to which they enjoyed the treatment, and the extent to which they feel their symptoms have changed as a result of treatment. Version 2 is to be included in the post/telephone follow-up questionnaires and contains only the questions about the extent to which the participant feels their symptoms have changed as a result of treatment.

4. Analysis

Describe any qualitative tests and measures as well as quantitative methods:

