All data will be anonymized and analyzed using non-parametric and parametric standard tests using SPSS software. Statistical analyses will be performed with appropriate correction for multiple comparisons.

The endpoints will be the post-treatment clinical assessment session.

Scores for each of the outcome measured will be analyzed using two-by-two, repeated measures ANOVAs, with Group (sham, prism) and session (pre, post) as independent factors. In the case of the self-report measures, two-by-four repeated measures ANOVAs will be performed with Group (sham, prism) and session (pre, post, one-month, three-months) as independent factors. Post hoc analyses will be in the form of t-tests (or non-parametric equivalents), corrected for multiple comparisons. These tests will determine if prism adaptation improves performance to a greater extent than sham treatment. In addition, 95% confidence intervals will be constructed around mean performance for each group before and after sham or prism treatment to test whether the group performance deviates significantly from established normative data or diagnostic cut-offs (e.g., for the UPDRS).

5. Study Progress Monitoring

Note: appropriate monitoring may include periodic assessment of the following:

- data quality
- timelines
- recruitment and enrollment

Provide a description of the methods which will be used to determine the progress of the study, including periodic assessments of data quality, timelines, recruitment, and enrollment as appropriate:

We will check into using the psychiatry DSMB.

6. Risks & Benefits

Note: Risks may be physical, psychological, social, legal, economic, to reputation, or others.

a. Describe any potential risks, their likelihood and seriousness:

There is a minor risk that the treatment or assessment procedures will result in some fatigue or discomfort. This is expected to be short-lived, and would be no greater than that involved in patients' normal physical therapy. To minimize the risk of fatigue during the pre- and post-treatment assessments, patients will be provided with breaks between tasks as required. Prism adaptation has been used for studying sensory-motor integration in healthy individuals for over a century, and in the treatment of stroke patients with hemispatial neglect for over ten years. In this time there have been no reports of serious adverse effects.

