Yes, the study is based on the premise that a link between a genotype or a biomarker and a specific disease or condition is clinically useful in predicting the development of that specific disease or condition. **Please complete the [Genetic Research Form](#) and upload it to the ‘Supporting Documents’ page in Rapport.**

-OR -

Yes, the study is looking for an association between a genotype or a biomarker and a specific disease or condition, but at this point it is not clear if the genetic marker has predictive value. The uncertainty regarding the predictive value of the genetic marker is such that studies in this category will not involve referral of participants to genetic counseling; however, participants will be informed of genetic testing in the consent form. **Please comment:**

10. Equitable Participant Selection

a. Estimated number of participants at Dartmouth CPHS reviewed sites:

Approximately 30 patients will be enrolled in the study at Dartmouth-Hitchcock Medical Center.

b. Provide a justification of the proposed sample size

For the methods specified above, there is no well-established method for calculation of group size as yet. We can, however, draw on experience from previous experiments, indicating what is the minimal/optimal number of participants for detecting significant effects. Previous studies that tested the effects of a similar prism adaptation treatment protocol on sensory and motor problems in stroke patients have used between 12 and 16 patients per group (Frassinetti, Serino). We aim to approach 40 patients with at least 32 completing the study (16 per group), which will provide a sufficient dataset even if up to 20% of participant withdraw before the completion of the study

c. Define the target population:

The patient population that will be targeted are the patient is referred for Parkinson's disease with gait impairment at Dartmouth-Hitchcock Medical Center

Inclusion/Exclusion Criteria:

Inclusion

- Diagnosis of idiopathic Parkinson's Disease
- Referral for gait training
- Aged 40-85
- If the subject is taking CNS-acting CNS-acting medications (benzodiazepines, hypnotics, antidepressants), regimen must be stable for 30 days prior to baseline visit
- Subjects with Stage II.5 – Stage IV (Hoehn and Yahr scale) where stage II.5 is bilateral involvement with axial involvement, but without balance difficulty, to Stage IV where one has severe disability but is still able to walk or stand unassisted.

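### Allocation may be steered to match groups on symptom severity, but no planned model includes severity; so far as severity predicts the quantity analysed, the unadjusted test is conservative.

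*Combined protocol and SAP*

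**What the plan says.** Section 3, Randomization and blinding, starts from a pre-generated pseudorandom sequence but adds that "deviations from this sequence may be made in order to ensure that the two groups are approximately matched in severity of symptoms". It names no severity scale, threshold or algorithm.

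Section 4 analyses the clinical and mechanized outcomes by two-by-two ANOVA "with Group (sham, prism) and session (pre, post) as independent factors". For the self-report outcomes, "two-by-four repeated measures ANOVAs will be performed with Group (sham, prism) and session (pre, post, one-month, three-months) as independent factors". Follow-up tests are also unadjusted: "Post hoc analyses will be in the form of t-tests (or non-parametric equivalents), corrected for multiple comparisons". The stated aim is comparative improvement: "These tests will determine if prism adaptation improves performance to a greater extent than sham treatment".

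The only covariate named anywhere is patient expectation (Section 3, Self-report questionnaires), to be used post hoc to "regress out any potential effects of patient expectation (e.g. placebo effect) on perceived improvements".

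**The concern.** Forcing two groups to agree on a factor that predicts the analysed quantity reduces the true variance of the difference between them. A model that omits the factor leaves its contribution in the residual and computes the standard error as if balance had been left to chance. The interval is then too wide and the test rejects less often than its nominal level. In a trial of 30 to 40 patients with no power calculation, that matters if the effect is sizeable and the remedy is cheap.

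The question is whether this reaches the test that answers the treatment question, which is the Group x session contrast rather than a comparison of post-treatment levels.

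**Working it through.** **The plan's own figure.** Section 10b approaches 40 patients and expects at least 32 completers, 16 per group, "even if up to 20% of participant withdraw before the completion of the study". 40 x 0.8 = 32, so this reproduces. The plan gives no SD, power target or test level, so nothing else can be reproduced.

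**Inputs.** From Section 10b: 16 per group. Assumed: two-sided 5% level; within-group SD of change set to 1; effect 0.8 SD; r, the correlation of severity with change, from 0 to 0.5.

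**Model.** In the two-by-two design, the Group x session test is the two-sample t-test on change (post minus pre). Any part of severity that is the same at both sessions cancels. Only its link with change remains: change = effect x group + r x severity + noise, with noise variance 1 - r².

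**Standard error under exact balance.**
- Reported by the unadjusted test: about √(2/16) = 0.354.
- True: √((1 - r²) x 2/16). At r = 0.5 this is 0.354 x 0.866 = 0.306, so the reported value is 1/0.866 = 1.155 times the true one, about 15% too wide.
- Type I error ≈ 2 x P(T on 30 df > 2.042/√(1 - r²)). At r = 0.3: 2.042/0.954 = 2.141, giving 4.0%. At r = 0.5: 2.042/0.866 = 2.358, giving 2.5%.

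**Simulated type I error, unadjusted Group x session test.**

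| Allocation assumed | r = 0 | r = 0.3 | r = 0.5 |
|---|---|---|---|
| 1:1 randomization, no steering | 5.1% | 5.4% | 5.0% |
| Neighbouring-severity pairs split at random | about 5% | 4.2% | 2.4-2.7% |
| Sequential, always towards balance | 5.0% | 4.0% | 2.8% |
| Sequential, 70% of assignments towards balance | 4.6% | 4.5% | 2.8% |
| Override only if means would differ by over 0.5 SD; 40 allocated, 32 complete | not run | 4.7% | 3.9% |

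A further sequential run gave 3.6-4.2% at r = 0.3 and 2.5-3.2% at r = 0.5. With severity as a covariate, the test stays near 5% throughout. The sign of r does not matter for this test.

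**Power for a 0.8 SD effect, unadjusted against adjusted.** The unadjusted noncentrality is 0.8/0.354 = 2.263, which gives 59%. Adjustment divides it by √(1 - r²), to 2.372 at r = 0.3 (63%) and 2.613 at r = 0.5 (71%). Simulation agrees:

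| | r = 0.3 | r = 0.5 |
|---|---|---|
| No steering | 59% vs 61% | 60% vs 70% |
| Severity pairs | 59% vs 63% | 60% vs 71% |

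At r = 0 the two tests have equal power. At r = 0.5, 10 of the 11 points appear without any steering; at r = 0.3, about 2 of 4.

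**Could r be other than zero?** If the matching scale is also the outcome, with equal pre and post variances and pre-post correlation ρ, then r = -√((1 - ρ)/2). For ρ from 0.5 to 0.9, r runs from -0.50 to -0.22, and type I error under perfect balance from 2.5% to 4.5%. The UPDRS motor score is an outcome and a plausible matching scale, but the plan does not say that it is used.

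**Tests on levels.** With an assumed severity-baseline correlation of 0.7, r = 0 and full steering, type I error is about 2.3% for a t-test on post scores and 1.3% for the Group main effect. For post scores this fades if sicker patients improve more: 3.9% at r = -0.3 and 4.8% at r = -0.5.

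**The case against.** The strongest reply is that each patient is their own control, so a stable severity effect drops out of the treatment test. This stands. If severity does not predict change, the planned test is correctly calibrated and adjustment gains nothing, and the documents give no such correlation. A reader might infer that the planned test is certainly conservative; the text supports only the conditional statement.

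A reader might also infer that steering costs power, or that the gap between the adjusted and unadjusted tests comes from ignoring the matching. Neither follows. Unadjusted power is about 59-60% with or without steering, and at r = 0.5 nearly all the gain from adjustment is what any prognostic covariate would bring.

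The matching is discretionary and approximate, so perfect pairing overstates its tightness. A loose override gives 3.9% rather than about 2.5% at r = 0.5, which narrows the problem without removing it. Finally, the error is on the safe side: this mechanism does not inflate false positives.

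What remains is that Section 4 does not say which ANOVA term or follow-up t-test decides the comparison. Section 1 reports that impaired forward body movement, a hypothesized outcome, correlates with symptom severity. Tests on levels, if used, are therefore exposed even when severity does not predict change.

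**Conclusion.** The point holds conditionally. Severity can influence allocation, no planned model contains it, and the unadjusted standard error is too large to the extent that severity predicts change, or predicts level where levels are tested. For the Group x session test with 16 per group, type I error is about 5% at r = 0, 3.6-4.7% at r = 0.3 and 2.5-3.9% at r = 0.5. These figures rest on assumed correlations, an assumed two-sided 5% level and assumed forms of steering.

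The power gain from adjustment is real but is largely ordinary covariate efficiency. The plan's conflicting enrolment figures (about 30 in Sections 3 and 10a; 40 in Sections 1 and 10b) do not change the conclusion: 30 x 0.8 = 24, or 12 per group, and the mechanism is the same. This is an inexpensive improvement to the analysis, not a threat to the validity of a positive result.

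**What to change.** In Section 4, name the one pre-treatment severity score that guides allocation, recorded before the goggles are issued, and include it in the parametric group comparisons. Suggested wording: *The severity score used in allocation is [scale]; its pre-treatment value is a covariate in every parametric comparison of prism with sham.* This can be an ANCOVA on change or on post score, or severity plus severity x session in the two-by-two and two-by-four models. The interaction is needed because severity alone does not enter the Group x session contrast.

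Where a non-parametric test is needed, use a rank-based ANCOVA, or report the unadjusted test as a sensitivity analysis.

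The cost is one degree of freedom in the ANCOVA, or two in the two-by-two repeated-measures form (one between and one within patients); with four sessions the interaction takes three. No new data should be needed: Hoehn and Yahr stage and MDS-UPDRS Part III items are eligibility measures, and the UPDRS motor score is taken at pre-test. The sponsor does have to decide which scale is meant.

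The covariate does not repair the risk of selection bias when an unblinded allocator may override the sequence. That needs its own remedy in Section 3.

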We previously tested the hypothesis that adaptation to upward-shifting prisms, producing a downward recalibration in pointing, would reduce forward stepping time in patients with Parkinson's disease. The rationale for this approach was that, based on the results of Tilikete and colleagues, adaptation to upward-shifting prisms would shift the standing posture forwards. In a study of 16 patients we found that a single five-minute session of prism adaptation reduced forward stepping time by an average of 183ms (~10% reduction) [4]. Backward stepping time was unchanged, and a test of adaptation to downward-shifting prisms with control participants showed no effect on forward or backward stepping. This study provides proof-of-concept that prism adaptation can reduce forward stepping time in patients with Parkinson's disease using a laboratory-based measure of stepping.

2. Objectives and Hypotheses

Objective: To compare the effect of two weeks of twice-daily adaptation to upward prismatic shifts in the visual field vs. two weeks of sham adaptation on measures of posture and gait in patients with idiopathic Parkinson's Disease.

Hypotheses: Compared to patients who undergo sham prism adaptation, patients who complete two weeks of real prism adaptation therapy will show reduced stepping initiation times, greater displacement of the body over the feet during stepping initiation, and increased self-report of confidence while walking. We will also measure a number of other common clinical indicators to determine whether prism adaptation improves motor performance and postural responses to external perturbations.

3. Study Design

Describe all study procedures, materials, and methods of data collection:

The study will have a longitudinal, repeated-measures, between-subjects, double-blind, sham-controlled design. Thirty patients with idiopathic Parkinson's Disease will be randomly assigned to undergo two weeks of twice-daily sessions of adaptation to upward-shifting prisms, or sham adaptation (in which patients perform the same sensory-motor task while wearing goggles fitted with neutral lenses). Measures of posture and gait (see below) will be recorded in two sessions: pre- and post-treatment. Additional long-term follow-up will be obtained through questionnaires by mail at one week, one month and three months post-treatment. The timeline for the research sessions, intervention period and follow-up questionnaires are outlined in Figure 1.

Procedures:

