Patients will undergo self-guided adaptation sessions in their own home, after initial training in the adaptation procedure by [name]. Patients in the experimental condition will receive goggles fitted with prismatic lenses that induce a 15° upward shift in the visual image. Patients in the control condition will receive goggles fitted with neutral lenses. For each prism/sham adaptation session, patients will sit in a chair within reaching distance of a wall or cabinet upon which two dime-sized targets will be placed (one above the other, approximately ten inches apart). While wearing the goggles, patients will point rapidly to one target then the next, bringing their hand back to their torso between each pointing movement. They will be instructed to perform these movements ‘as quickly as possible’ for a total of 50 pointing movements (<5 minutes) in each treatment session. After performing 50 pointing movements the will remove the goggles. Each patient will undergo two daily sessions of prism adaptation for 14 consecutive days.

Assessment of Posture and Gait

Assessments of posture, gait, and activities of daily living will be performed by a Neurologist and a trained Physical Therapist at the Dartmouth-Hitchcock Medical Center on two occasions immediately before and immediately after the intervention period (the pre- and post-test). Three categories of outcome measures will be used; standard clinical assessments, mechanized measurements, and self-report questionnaires will be conducted by mail and/or phone on three further occasions (one week, one month and three months post treatment).

1) Standard clinical assessments.

Four commonly used clinician-scored evaluations will be used.

General Neurological Examination. This will be performed by a trained neurologist, and involves simple sensory and motor tests.

The Unified Parkinson’s Disease Rating Scale (motor component). Several dimensions of motor control are assessed by a clinician-scored evaluation. Patients are asked to perform simple tasks such as tapping their fingers as quickly as possible for five seconds, and their performance on each item is scored on a scale of 0 (“normal”) to 4 (“can barely perform the task”). The total score out of 92 is computed.

Timed Up and Go test. Starting from a seated position, the person is required to stand up, walk to a line 10 meters away, turn around, walk back and sit down. The person is timed.

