Functional Gait Assessment. This is a reliable and valid assessment of assessing ten gait-related measures (e.g. stepping over a box, climbing stairs). A total score out of 30 is calculated, with lower scores indicating greater impairment.

2) Mechanized measures

We will use two sophisticated measurement systems to measure musculoskeletal factors related to posture and gait.

Assessment of postural stability using the SMART EquiTTest Balance Master. This system uses a force plate to measure center of gravity and postural control. Patients stand on a force plate while wearing a support vest. We will use two protocols provided by this system. The Motor Control test assesses the ability of the patient to recover their standing balance after an unexpected translation of the force plate. The Limits of Stability test measures the maximum distance a person can intentionally displace their center of gravity in a given direction without losing balance, stepping or reaching for their center of gravity in a given direction without losing balance, stepping or reaching for assistance. For both of these tests a comprehensive performance report is provided, including measures of reaction time and amplitude of movements.

We will also perform a third test that is not part of the standard EquiTTest protocol. For this, we will ask participants to take a step forward. We will measure the displacement of the center of gravity over the center of pressure (i.e., the movement of the body over the feet) using the same performance report as is used for the Limits of Stability test. This non-standard test will allow us to directly test our hypothesized mechanism of prism adaptation treatment: namely that it increases the displacement of the body over the feed when patients initiate walking.

Assessment of gait using the ActiveStep. This system is a mobility stimulator that enables safe measurement of walking and propensity to fall with and without environmental perturbations. A number of parameters are measured, including trunk extension and flexion velocity and step length and speed.

3) Self-report questionnaires

Four questionnaires will be used to measure patients' perceptions of their risk of falling and their confidence in safely performing daily activities. These will be administered five times: in the pre-test, post-test, one-week follow-up, one-month follow-up, and three-month follow-up.

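### The self-report ANOVA omits the one-week form without a reason, has no rule for missing forms, and names no contrast at the post-treatment endpoint

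*Combined protocol and SAP*

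**What the plan says.** Section 3 (Study Design) plans follow-up "questionnaires by mail at one week, one month and three months post-treatment". Its self-report subsection says of the four questionnaires: "These will be administered five times: in the pre-test, post-test, one-week follow-up, one-month follow-up, and three-month follow-up". The subsection on assessment of posture and gait lists the same three later occasions and allows collection by mail or telephone.

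Section 4 (Analysis) gives most outcomes a two-by-two ANOVA (Group by pre/post). For the self-report measures it then says "two-by-four repeated measures ANOVAs will be performed with Group (sham, prism) and session (pre, post, one-month, three-months) as independent factors". The same section states: "The endpoints will be the post-treatment clinical assessment session". On follow-up testing it says: "Post hoc analyses will be in the form of t-tests (or non-parametric equivalents), corrected for multiple comparisons". The next sentence reads: "These tests will determine if prism adaptation improves performance to a greater extent than sham treatment".

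Section 10b aims for 40 patients approached and at least 32 completing (16 per group), allowing for up to 20% withdrawal. That is the only statement on attrition. It concerns numbers to recruit, not how an incomplete series is analysed.

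**The concern.** Increased self-reported walking confidence is one of the three stated hypotheses in section 2, and that section gives it no time point. The analysis leaves three things open.

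- **One-week wave.** It is collected but has no place in the analysis. The documents do not show whether this is deliberate or a slip. Left open, the choice could be made after data have been seen, and the plan unblinds most of the team to completed patients' groups at the 60% look.
- **Missing forms.** A conventional repeated measures ANOVA needs a score at every session. The plan does not say it will be run that way, but offers no alternative rule.
- **Endpoint.** The test implied by a two-by-four layout is Group by session on 3 degrees of freedom. It responds to any departure from parallel profiles, whenever it occurs, whereas the stated endpoint is a single session.

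At stake is whether a self-report result can be read as an answer at the stated endpoint, and from which patients.

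**Working it through.** **The plan's own figure.** 32 / (1 − 0.20) = 40, which matches section 10b. No power, effect size, correlation or return rate is given for the self-report scales, so everything below rests on assumed values. (Sections 3 and 10a give 30 patients instead of 40; that is a separate matter.)

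**1. Schedule against analysis.**

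| | Pre | Post | 1 week | 1 month | 3 months |
|---|---|---|---|---|---|
| Collected (section 3) | yes | yes | yes | yes | yes |
| In the ANOVA (section 4) | yes | yes | no | yes | yes |

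One of the three remote waves has no analysis.

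**2. Retention in a complete-case two-by-four.** Start from 32 patients with pre and post data. Let *p* be the return rate of each of the two later forms used. Independent misses keep 32*p*²; if the same patients miss both forms, 32*p* stay.

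| Return per form | Independent misses | Same patients miss both |
|---|---|---|
| 95% | 32 × 0.9025 = 28.9 | 30.4 |
| 90% | 32 × 0.81 = 25.9 | 28.8 |
| 85% | 32 × 0.7225 = 23.1 | 27.2 |

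If every form is returned, 32 stay. Simply adding the one-week form to the same ANOVA would, with independent misses, leave 32 × 0.9³ = 23.3 at 90% or 32 × 0.85³ = 19.7 at 85%.

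**3. What the interaction test responds to.** Assume 16 per group, a difference of 0.7 SD, equal variances, equal correlations ρ and two-sided 5%. The noncentrality is (16/2) × Σ(δⱼ − δ̄)² / (1 − ρ), where δⱼ is the group difference at session j, with 3 and 90 df.

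- Effect at post only, (0, 0.7, 0, 0): the mean is 0.175, so Σ = 0.525² + 3 × 0.175² = 0.3675.
- Effect at three months only, (0, 0, 0, 0.7): Σ is the same, 0.3675.
- Sustained effect, (0, 0.7, 0.7, 0.7): Σ is again 0.3675.

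For ρ = 0.5/0.7/0.8 the noncentrality is 5.88/9.80/14.70 and power is 0.49/0.73/0.90 in all three cases. The exact equality depends on the equal-correlation assumption. That the test is not specific to one session does not.

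**4. Power of a test aimed at post, complete data, same assumptions.**

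- Pre/post change t-test, 30 df: noncentrality 0.7 × √8 / √(2(1 − ρ)) = 1.98/2.56/3.13; power 0.48/0.70/0.86.
- Baseline-adjusted post-test contrast, 29 df: noncentrality 0.7 × √8 / √(1 − ρ²) = 2.29/2.77/3.30; power 0.60/0.76/0.89.

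Against the two-by-four, the adjusted contrast gains about 11 points at ρ = 0.5 and 3 at 0.7, and loses about 1 at 0.8. The gain over the change test comes from baseline adjustment, not from handling missing data. These are ANCOVA figures; the mixed model itself was not simulated.

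**5. Selective loss, for analyses restricted to complete series.** Suppose patients with no observed pre/post gain miss each later form more often than the others. By simulation, a true 0.70 SD difference in change becomes about 0.62 SD (30% against 5% missed), 0.66 (20% against 5%) or 0.67 (20% against 10%). The shift is 0.03 to 0.08 SD, toward the null. The standard error of the change difference at 16 per group is √(2(1 − ρ) × 2/16) = 0.35/0.27/0.22 SD, so the shift is roughly a tenth to a third of one standard error.

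**The case against.** The strongest reply is that section 4 does not stop at the ANOVA. It plans corrected post hoc t-tests and assigns the question of benefit over sham to tests described at that point. A pre/post t-test needs no later form, keeps every patient with both visits, and could locate an effect at post-test. This stands. A reader might infer that patients are bound to be lost from the post-test comparison, or that the plan cannot show benefit at post-test at all; the documents support neither. What remains is that the t-tests are tied to no session, pair or change score.

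The endpoint sentence refers to the clinical assessment session, and the confidence hypothesis has no time point, so self-report may have been meant to be judged across follow-up. That is possible, and the two-by-four would then fit better. But the plan does not say so, the questionnaires are given at the post-test, and the only endpoint it names is that session.

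The retention figures may also subtract attrition twice. The 32 are described as completing the study, follow-up runs to three months, and telephone collection may raise return. Hence the range includes no loss.

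Finally, one might infer that the two-by-four wastes power on extra degrees of freedom. The calculation does not bear this out: with complete data the change test has similar or slightly lower power.

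**Conclusion.** The concern holds in limited form, at low to moderate severity. Three gaps rest on the text alone: an unexplained one-week omission, no rule for missing forms, and no stated contrast at the named endpoint. The 3-df test does not by itself show benefit at post-test.

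The consequences are conditional. Loss over later forms applies to a complete-case two-by-four, or to t-tests confined to its completers. Across assumed returns of 95% to 85%, retention runs from about 29 to 23 of 32 with independent misses, about 30 to 27 if the same patients miss both forms, and 32 with full return. Selective-loss bias is confined to the same restricted analyses and is modest under the assumed rates. A stronger claim, that the post-test result is biased as planned, is not supported, because no section restricts the t-tests to complete series.

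**What to change.** For the self-report measures, replace the two-by-four ANOVA with a linear mixed model on all available post-test, one-week, one-month and three-month scores. Include Group, session, Group by session, the pre-test score and pre-test by session. Choose a covariance structure that about 30 patients can support, for example unstructured with a named fallback such as compound symmetry, and use Kenward-Roger or Satterthwaite degrees of freedom. Name the prism-minus-sham difference at post-test as the endpoint contrast, in line with section 4, and report the later differences as durability.

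If the ANOVA is kept, the minimum is to say why one week is left out, how missing forms are handled, and which sessions the post hoc t-tests compare.

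The cost is analysis wording only, with no extra data, visits or forms. The downside is that the model assumes data are missing at random, so dropout that depends on unobserved lack of benefit could still bias the later waves.
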